7.1.10. Missing data

1. Days with missing data will not be ignored when defining start of an **e-diary** signal: e.g., if a patient has two qualifying symptoms followed by a missing day, if the next day with data has two qualifying symptoms this will not be defined as an exacerbation. Hence, the start of an **e-diary** signal of an exacerbation will require 2 consecutive non-missing days of worsening. If there is partially recorded symptom data at a visit, however, only the observed values will be considered but the day will not be discarded.
2. Days with missing data will be ignored when defining end of an **e-diary** signal of an exacerbation: e.g., if a patient has two days missing in the baseline period and one day missing in the 3- day moving average, both baseline and 3-day moving average values will be calculated using observed data only. Similar rules will apply when there is partially recorded symptom data at a visit (and daily average values will be calculated among the observed values).
3. All available data will be used for each patient.
4. As a general rule, the baseline symptom count score, and 3 day moving averages are calculated as the average count score of the observed days in the baseline period. For example, if an **e-diary** signal occurs from day 10 onwards, the baseline period will be the average between day1 and day2 (day1 being the first study day). If day 13 is missing, the 3 day moving average at day 14 will only take into account day 14 and day 15.
5. If there are greater than 2 consecutive days of missing data after an **e-diary** signal not resolved, the **e-diary** signal will not be considered resolved until the next day with observed data if the corresponding moving average is below the baseline value. In other words, if the 3-day average daily score is missing, the day will be counted in the duration of the episode.

7.1.11. AECOPDs definitions and calculation rules

7.1.11.1. AECOPD definition (from clinical evaluation)

Due to the sensitivity and specificity of the e-diary device, false alerts may occur, and exacerbations resulting in site visits may also occur without e-diary alert. Therefore, only unscheduled AECOPD visits with clinical confirmation of AECOPD (with or without associated signals) will be considered as AECOPD events in the primary analysis.

In addition, missed AECOPD visits may have occurred and can be:

Statistical Analysis Plan

Study alias & e-track number(s): NTHi-004 (200157)

- *a signal from the e-diary (PHT) without a site visit but that cannot be discounted as a possible exacerbation signal after reconciliation,*
and/or
- *an exacerbation reported retrospectively in the Safety database or medical records for which there has not been in the same period of retrospective reporting a corresponding exacerbation visit declared.*

7.1.11.2. Characterization of inconsistencies between morning e-diary signals and exacerbation site visits

The reconciliation between morning e-diary (PHT) signals and site visits for exacerbation will aim at characterizing the following 2 cases:

Case A : an e-diary alert with absent/delayed exacerbation visit (i.e. no exacerbation visit within the calculated length of the e-diary episode)

Case B : a exacerbation visit with absent/delayed e-diary exacerbation alert (i.e. RDE exacerbation not within e-diary exacerbation period)

The different reasons of inconsistencies of Case A will be categorized by the site after review according to the following explanation:

- 1) *Not an exacerbation after further evaluation* : eg. when a patient does not feel well but this is due to increased exercise, or patient does not feel well but this is not clinically significant.
- 2) *Ongoing exacerbation* : e.g., previous exacerbation is not terminated according to the clinician.
- 3) *RDE or other technical issues*: e.g., due to technical issues e-diary alerts were not sent and when the site was aware of it was too late to determine whether this was an exacerbation or not.
- 4) *Other reasons: specify* : e.g. subject was on holidays / subject unable to visit the site / delayed RDE visit/early RDE entry.

The different reasons of inconsistencies of Case B will be categorized by the site after review according to the following explanation:

- 5) *Spontaneous visit clinically deemed exacerbating* i.e. exacerbation visit took place before the e-diary alert (spontaneous visit, visit triggered by GP / Patient call asked to be seen/ felt too unwell to complete e-diary abrupt onset)
- 6) *Planned monthly visit clinically deemed exacerbating*

Statistical Analysis Plan

GlaxoSmithKline

Study alias & e-track number(s): NTHi-004 (200157)

7) *e-diary diary card recording issue or other technical issues* : e.g. late e-diary alerts, subject missed or did not correctly record diary card, broken log pad device.

8) *Other reasons: specify*

For a Case A, no laboratory data has been collected, but if the answer about the inconsistency is 3) or sometimes 4) (depending on the specification), it will qualify as AECOPD. All Cases B will be considered to be an AECOPD if the AECOPD is confirmed by the site.

7.1.12. Grading of severity of an exacerbation

Severity of exacerbations is defined as (Protocol Section 5.3.1.2):

- Mild: Worsening symptoms of COPD that are self-managed by the patient.
- Moderate: Worsening symptoms of COPD that require treatment with oral corticosteroids and/or antibiotics.
- Severe: Worsening symptoms of COPD that require treatment with in-patient hospitalisation or home care intervention.

Severity of the exacerbation will not be derived but taken directly from the information entered in the CRF.

7.2. Data presentation description

The following decimal description will be used for the demography and safety/reactogenicity.

Display Table	Parameters	Number of decimal digits
All summaries	% of count, including LL & UL of CI	1
All summaries	% of difference, including LL & UL of CI	2
Demographic characteristics	Mean, median age	1
Demographic characteristics	SD (age)	2
Immunogenicity	GMT ratio	2

The following data presentation description will be used for the immunogenicity analyses.

Component	GMC/T	Assay		Assay cut-off	Number of decimal digits		Tick marks on RCC's		
		method	Unit		GMC/T	GMC/T ratio			
					Low value	High value			
Anti-PD	GMC	ELISA	EL.U/mL	100	1	2	1	10000	
Anti-PE	GMC	ELISA	EL.U/mL	8	1	2	1	10000	
Anti-PiLA	GMC	ELISA	EL.U/mL	7	1	2	1	10000	

Statistical Analysis Plan

Study alias & e-track number(s): NTHi-004 (200157)

8. CONDUCT OF ANALYSES

8.1. Sequence of analyses

The analyses will be performed stepwise:

- The analysis of data up to Visit 6 (Day 90) will be performed in a first step. This analysis will include:
 - The final analysis of immunogenicity and solicited AEs post-Dose 1 and post-Dose 2.
 - The assessment of unsolicited AEs, SAEs and pIMDs up to 30 days post-Dose 1 and post-Dose 2 on as cleaned as possible data.

This analysis will be documented in a statistical report. At this point, the GSK statistician of the project (or delegates) will be unblinded (*i.e.* will have access to the individual subject treatment assignments).

- The final analysis of data up to study conclusion will be performed in a second step, once those data will be available and cleaned. This analysis will include:
 - The final analysis of immunogenicity at Day 270 and Day 450.
 - SAEs and pIMDs up to Day 450 on cleaned data.
 - Impact of the investigational vaccine on AECOPD, HRQOL, lung function, exercise capacity and biomarkers.

In addition, all previous analyses will be re-produced based on cleaned data at this point.

Individual listings will only be provided at this stage. A final study report containing data from the entire study will be written and will be made available to the investigators.

Description	Analysis ID (SDD & CARS sub-folder)
Analysis up to Visit 6 (Day 90)	E1_06
Final analysis (up to day 450)	E1_01

8.2. Statistical considerations for interim analyses

Not applicable.

Statistical Analysis Plan

GlaxoSmithKline

Study alias & e-track number(s): NTHi-004 (200157)

9. CHANGES FROM PLANNED ANALYSES

As during the study, some subjects have completed wrong diary cards (paediatric ones instead of adults), a sensitivity analysis will be done on subjects that have completed the correct diary cards to be sure that they were no impact on results.

ICS	Intracellular cytokine staining

Statistical Analysis Plan

Study alias & e-track number(s): NTHi-004 (200157)

IU/ml	International units per milliliter
LL	Lower Limit of the confidence interval
MA	Internal GSK database code for Main analysis (elimination codes) link to FORM-BIO-CLIN-9004-05 Criteria for eliminating subjects from the analyses
MATEX	MATerial EXcellence
M. catarrhalis	Moraxella catarrhalis
MedDRA	Medical Dictionary for Regulatory Activities
mMRC scale	mMRC scale
N.A.	Not Applicable
NTHi	Non-Typeable Haemophilus influenzae
PBMC	Peripheral blood mononuclear cell
PCR	Polymerase chain reaction
PD	Protein D
PE	Protein E
PI	Prescribing information
PilA	Type IV pili subunit of non-typeable Haemophilus influenzae
pIMD	Potential immune-mediated disease
PT	Preferred term
SAE	Serious adverse event
S. aureus	Staphylococcus aureus
SAP	Statistical Analysis Plan
SBIR	GSK Biological's Internet Randomization System
SD	Standard Deviation
SR	Study Report
STGG	Skim milk, tryptone, glucose, and glycerin transport medium
SYN	Synopsis
TFL	Tables Figures and Listing template annexed to SAP
TVC	Total vaccinated cohort
UL	Upper Limit of the confidence interval
VE	Vaccine efficacy

Statistical Analysis Plan

Study alias & e-track number(s): NTHi-004 (200157)

6MWT

6-Minute Walk Test

Statistical Analysis Plan

Study alias & e-track number(s): NTHi-004 (200157)

The complete statistical analysis plan and results presentation is divided into 2 parts: the first part detailing the analyses to be performed (known as SAP, current document) and a second part, annex (-es) (called TFL) describing the flow and format of tables, figures and listings to be annexed to the SR.

1. DOCUMENT HISTORY

Date	Description	Protocol Version
29-JAN-2016	Version 1	Amendment 2 - 15-DEC-2014
21-JUN-2016	
Amendment 1
 
In order to see early effects of the vaccine on the microbiome, analysis on fresh sputum samples (culture results) will be done on all available data up to the data lock point of the interim analysis.
 
In order to have a first look whether or not the investigational vaccine has an impact on AECOPD, AECOPD analyses will be done up to the data lock point of the interim analysis
	Amendment 3 - 15-APR-2016

Statistical Analysis Plan

Study alias & e-track number(s): NTHi-004 (200157)

2. STUDY DESIGN

Figure 1 Study design overview

[figure not shown]
$N \geq 70/\text{group}$

40 – 80 years

10-30 years
COPD patients

10 μ g Ag/ AS01 E

108

Scr = Screening; **V** = Visit; **D** = Day; **rando** = randomisation; **VACC** = vaccination; **BS(1)** = blood sample for safety; **BS(2)** = blood sample for humoral immunogenicity; **BS(3)** = blood sample for cell-mediated immunity (CMI); **BS(4)** = blood sample for biomarkers; **SP** = sputum sample

In addition to the scheduled study visits depicted above, **ad hoc AECOPD-driven study visit(s) and/or phone contact(s)** will take place for each AECOPD occurring from first vaccination up to study conclusion. An AECOPD visit will be scheduled as soon as possible after the onset of AECOPD symptoms (maximum 96 hours after and, if applicable, preferably before starting treatment with antibiotics). In addition, follow-up phone call(s) and/or visit(s) will take place to determine the end of the AECOPD. These contacts will take place at least every 2 weeks, until the AECOPD has resolved.

Experimental design: Phase II randomised, observer-blind, placebo-controlled, multi-centre study with 2 parallel groups.

Duration of the study: for each subject enrolled, the study will last approximately 16 months from Visit 1 up to study end

The following group names will be used for the statistical analyses:

Group order in tables	Group label in tables	Group definition for footnote
1	10-AS01E	2 doses of AS01e adjuvanted vaccine containing 10 mcg of each antigen
2	Control	2 doses of saline solution

Statistical Analysis Plan

Study alias & e-track number(s): NTHi-004 (200157)

3. OBJECTIVES

3.1. Primary objective

- To describe the safety and reactogenicity of the investigational vaccine.

3.2. Secondary objective

- To describe the humoral and cellular immunogenicity of the investigational vaccine.

3.3. Tertiary objectives

- To explore the impact of the investigational vaccine on AECOPD.
- To explore the impact of the investigational vaccine on NTHi presence in sputum.
- To explore the impact of the investigational vaccine on health-related quality of life (HRQOL).
- To explore the impact of the investigational vaccine on lung function.
- To explore the impact of the investigational NTHi vaccine on exercise capacity.
- To describe selected biomarkers in stable COPD and during AECOPD.
- To collect blood and sputum samples for assay development, for disease diagnostic purpose, for lung microbiome analysis and/ or for additional evaluation of the immune responses to the investigational vaccine and to other potential pathogens involved in AECOPD.

4. ENDPOINTS

4.1. Primary endpoints

- Occurrence of each solicited local adverse event (AE), during the 7-day follow-up period (*i.e.* day 0 - 6) following each vaccination, in all subjects.
- Occurrence of each solicited general AE, during the 7-day follow-up period (*i.e.* day 0 - 6) following each vaccination, in all subjects.
- Occurrence of any unsolicited AE, during the 30-day follow-up period (*i.e.* day 0 - 29) following each vaccination, in all subjects.
- Occurrence of each haematological/ biochemical laboratory abnormality at Day 0, Day 7, Day 30, Day 60, Day 67, Day 90, Day 270 and Day 450, in all subjects.
- Occurrence of any potential immune-mediated disease (pIMD) from first vaccination up to study conclusion, in all subjects.

Statistical Analysis Plan

Study alias & e-track number(s): NTHi-004 (200157)

- Occurrence of any serious adverse event (SAE) from first vaccination up to study conclusion, in all subjects.

4.2. Secondary endpoints

- Anti-PD, anti-PE and anti-PiLA total IgG antibody concentrations as measured by ELISA, at Day 0, Day 30, Day 60, Day 90, Day 270 and at Day 450, in all subjects.
- NTHi-specific cell-mediated immune responses as measured by flow cytometry intracellular cytokine staining (ICS) (frequency of specific CD4⁺/CD8⁺ T-cells expressing two or more markers, such as IL-2, IL-13, IL-17, IFN- γ , TNF- α and CD40L), at Day 0, Day 90, Day 270 and at Day 450, in a sub-cohort of subjects.

4.3. Tertiary endpoints

- Number of cases of NTHi-associated moderate and severe AECOPD, over a period starting 1 month post-Dose 2 and lasting for 1 year, in all subjects.
- Number of cases of NTHi-associated AECOPD (any severity), over a period starting 1 month post-Dose 2 and lasting for 1 year, in all subjects.
- Number of cases of moderate and severe AECOPD (any cause), over a period starting 1 month post-Dose 2 and lasting for 1 year, in all subjects.
- Number of cases of AECOPD (any cause, any severity), over a period starting 1 month post-Dose 2 and lasting for 1 year, in all subjects.
- Time to first AECOPD, in all subjects.
- Assessment of EXACT-PRO score, daily at bedtime throughout the study, in all subjects.
- NTHi presence in sputum, at Screening, Day 90, Day 180, Day 270, Day 360 and Day 450, and from first vaccination to study conclusion for each AECOPD, in all subjects.
- Assessment of CAT score, at Screening, Day 270 and Day 450, and from first vaccination to study conclusion for each AECOPD, in all subjects.
- Assessment of SGRQ-C score, at Screening, Day 270 and Day 450, in all subjects.
- Assessment of mMRC scale, at Screening, Day 270 and Day 450, and from first vaccination to study conclusion for each AECOPD, in all subjects.
- Occurrence of rescue medication use, over a period starting 1 month post-Dose 2 and lasting for 1 year, in all subjects.
- Occurrence of healthcare use for AECOPD, over a period starting 1 month post-Dose 2 and lasting for 1 year, in all subjects.

Statistical Analysis Plan

Study alias & e-track number(s): NTHi-004 (200157)

- Assessment of FEV1% of predicted normal value at Screening, Day 270 and Day 450, in all subjects.
- Assessment of 6MWT score, at Screening and Day 450, in all subjects.
- Occurrence of selected biomarkers in a subset of blood samples, at Day 0 and Day 450, and from first vaccination to study conclusion for each AECOPD, in all subjects.
- Presence of respiratory viral pathogens in sputum (including respiratory syncytial virus, parainfluenza virus, enterovirus/ rhinovirus, metapneumovirus, influenza virus, adenovirus, bocavirus and coronavirus) at Screening, Day 90, Day 180, Day 270, Visit Day 360 and Day 450 and at each AECOPD visit from first vaccination to study conclusion, in all subjects.

5. STUDY POPULATION

The following study cohorts will be evaluated.

5.1. Total vaccinated cohort

The Total vaccinated cohort (TVC) will include all subjects with at least 1 study vaccine administration documented:

- A **safety** analysis based on the TVC will include all vaccinated subjects.
- An **immunogenicity/ efficacy** analysis based on the TVC will include all vaccinated subjects for whom immunogenicity/ efficacy data are available.

The TVC analysis will be performed per treatment actually administered at Dose 1.

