6.2.2.2. Treatment allocation to the subject

The treatment numbers will be allocated by dose.

6.2.2.2.1. *Study group and treatment number allocation*

The target will be to enrol approximately 140 eligible subjects who will be randomly assigned to the 2 study groups in a (1:1) ratio (approximately 70 subjects in each group).

Allocation of a subject to a study group at the investigator site will be performed using a centralised randomisation system on the internet (SBIR). The randomisation algorithm will use a minimisation procedure accounting for age (40 - 59 years or 60 - 80 years), number of moderate/ severe AECOPD in the previous year (< 2 or \geq 2) and GOLD grade (GOLD 2 or GOLD 3). All factors will have equal weight in the minimisation algorithm.

At Visit 1, before administration of vaccine Dose 1 to eligible subjects who signed and dated the ICF at the Screening Visit, the dedicated site staff will access SBIR. Upon providing the subject's age category (40 - 59 years or 60 - 80 years), number of moderate/ severe AECOPD in the previous year and his/ her GOLD grade, the randomisation system will determine the study group and will provide the treatment number to be used for the first dose.

The number of each administered treatment must be recorded in the eCRF on the Vaccine Administration screen.

When SBIR is not available, refer to the SBIR user guide or the SPM for specific instructions.

6.2.2.2.2. *Treatment number allocation for subsequent doses*

For each dose subsequent to the first dose, the dedicated study staff will access SBIR. Upon providing the subject identification number, the system will provide a treatment number consistent with the allocated study group.

The number of each administered treatment must be recorded in the eCRF on the Vaccine Administration screen.

When SBIR is not available, refer to the SBIR user guide or the SPM for specific instructions.

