5.4. ATP cohort for analysis of efficacy

The ATP cohort for analysis of efficacy will include all subjects in the TVC:

- Who met all eligibility criteria.
- For whom the administration route and site of the vaccines was according to protocol.
- Who complied with the vaccination schedule
- Who received the study vaccine according to protocol procedures.
- Not having received a medication/ product/ vaccine that may lead to elimination from the ATP analysis for efficacy.

The list of applicable elimination codes for each cohort can be found in the study specific form FORM-BIO-CLIN-9004-05 Criteria for eliminating subjects from the analyses.

Cohort	Elimination codes	Eli Type
ATP cohort for analysis of immunogenicity	1010-2500	MA

Statistical Analysis Plan

Study alias & e-track number(s): NTHi-004 (200157)

ATP cohort for analysis of efficacy	1010-2500	EF
ATP cohort for analysis of persistence of immunogenicity	1010-2500	FU

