6.1.3. Analysis of impact of the investigational vaccine on AECOPD incidence

The analysis will be performed on the ATP cohort for efficacy. If the percentage of vaccinated subjects excluded from the ATP cohort for efficacy is more than 10%, a second analysis based on the TVC will be performed to complement the first analysis.

The following incidence rates will be computed over a period starting 1 month post-Dose 2 and lasting for 1 year, with 95%CI:

- NTHi-associated moderate and severe AECOPD. (See definition in section 7.1.4)
- NTHi-associated all-severity AECOPD.
- All-cause moderate and severe AECOPD.
- All-cause, all-severity AECOPD.

Vaccine efficacy (VE) for AECOPD events will be defined as:

$$VE (AECOPD) = 1 - R_{vaccine} / R_{control}$$

with:

- $R_{vaccine}$ = average yearly incidence rate of AECOPD events per subject in the group 10-AS01E.
- $R_{control}$ = average yearly incidence rate of AECOPD events per subject in the Control group.

In case the 95% CI of the VE cannot be estimated, *e.g.* when no event is observed in the group 10-AS01E (leading to a VE of 100%), then an exact procedure will be used to estimate a VE and its 95% CI. This exact procedure will be based on the number of subjects with event instead of on the average number of event per subject in each group.

Statistical Analysis Plan

Study alias & e-track number(s): NTHi-004 (200157)

VE in the prevention of NTHi-associated moderate and severe AECOPD and its 95% CI will be calculated.

VE in the prevention of NTHi-associated all-severity AECOPD, of all-cause moderate and severe AECOPD and of all-cause, all-severity AECOPD and their 95% CI will also be calculated.

The 95%CI of the incidence rate will be computed using a model which accounts for repeated events. The Generalised linear model assuming the Negative Binomial distribution for the response variable with logarithm as link function, and the logarithm of time for follow-up as an offset variable will be used. In addition, the following covariates (as per randomization) will be taken into account:

- country,
- number of moderate/severe exacerbations reported in the 12 months prior to enrolment,
- COPD status at enrolment (derived by GSK from the Visit 1 spirometry results)
- Age (below or equal to median/above median)

If the model does not converge, the Poisson distribution will be used instead of the Negative Binomial one.

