7. STATISTICAL CALCULATIONS

7.1. Derived and transformed data

The study groups will be defined by treatment actually administered at Dose 1.

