7.1.3. Immunogenicity

- For a given subject and the analysis of a given immunogenicity measurement, missing or un-evaluable measurements will not be replaced.
- A seronegative subject is defined as a subject whose antibody concentration is below the assay cut-off value.
- A seropositive subject is defined as a subject whose antibody concentration is greater than or equal to the assay cut-off value.
- Antibody concentrations below the assay cut-off will be given an arbitrary value of half the assay cut-off for the purpose of geometric mean concentration (GMC) calculation.
- Calculation of the GMCs will be performed by taking the anti-logarithm in base 10 (anti-log10) of the mean of the log10 concentration transformations.

Statistical Analysis Plan

Study alias & e-track number(s): NTHi-004 (200157)

- The assay cut-off is the value under which there is no quantifiable result for which no accuracy and precision can be reported. For an assay with a specific 'cut_off' , numerical immuno result is derived from a character field (rawres):
 - If rawres is 'NEG' or '-' or '(-)', numeric result= cutt_off/2,
 - if rawres is 'POS' or '+' or '(+)', numeric result = cut_off,
 - if rawres is '< value' and value<=cut_off, numeric result =cut_off/2,
 - if rawres is '< value' and value>cut_off, numeric result =value,
 - if rawres is '> value' and value<cut_off, numeric result =cut_off/2,
 - if rawres is '> value' and value>=cut_off, numeric result =value,
 - if rawres is '<= value' or '>= value' and value<cut_off, numeric result =cut_off/2,
 - if rawres is '<= value' or '>= value' and value>=cut_off, numeric result =value,
 - if rawres is a value < cut_off, numeric result = cut_off/2,
 - if rawres is a value >= cut_off, numeric result = rawres,
 - else numeric result is left blank.
- All CI computed will be two-sided 95% CI.

Impact of the investigational vaccine on AECOPD

- For a given subject and the analysis of a given laboratory assay, missing or un-evaluatable measurements will not be replaced.
- Subjects who did not have any sputum collected during at least 1 AECOPD (if at least 1 AECOPD occurred) will not be taken into account for the NTHI-associated AECOPD analyses.

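### Efficacy analyses on the Total Vaccinated Cohort are grouped by the product given at Dose 1, so they stop being comparisons by allocated group if anyone is misdosed at Dose 1

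*SAP*

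**What the plan says.** SAP Amendment 1 section 5.1 defines one TVC for safety, immunogenicity and efficacy. Its efficacy part is not all randomised subjects: the "analysis based on the TVC will include all vaccinated subjects for whom immunogenicity/ efficacy data are available". Section 5.1 then sets the grouping for the whole cohort: "The TVC analysis will be performed per treatment actually administered at Dose 1". Section 7.1 makes the rule general: "The study groups will be defined by treatment actually administered at Dose 1". Protocol 11.5.1 and 11.6 carry the same two rules, so the documents agree with each other.

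For exacerbations (AECOPD) and VE, SAP 6.1.3 starts elsewhere: "The analysis will be performed on the ATP cohort for efficacy". Only if more than 10% of vaccinated subjects fall outside that cohort is it the case that "a second analysis based on the TVC will be performed to complement the first analysis". SAP 6.1.5 works the other way round for HRQOL, lung function and exercise capacity: the TVC comes first, without a trigger, and the ATP efficacy cohort is the possible second analysis.

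One entry condition for the ATP efficacy cohort (SAP 5.4) is "Who received the study vaccine according to protocol procedures". Protocol 6.2.2.2 allocates subjects 1:1, about 70 per group, by minimisation on age, exacerbation history and GOLD grade, through SBIR.

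**The concern.** Grouping by product received is the usual choice for safety. For efficacy it moves a misdosed subject from the group that the allocation procedure chose to the other one. Minimisation balances age, exacerbation history and GOLD grade for the groups as allocated, and random allocation is what protects against imbalance in factors nobody measured. If misdosing is related to risk, regrouping by product can bias the comparison.

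The ATP cohort does not fill the gap. A subject given the wrong product at Dose 1 has probably not been vaccinated according to protocol procedures and would be dropped. The plan then offers two treatments of that subject, removal (ATP) or transfer (TVC), and never analysis in the allocated group.

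**Working it through.** **Does the rule reach efficacy?** SAP 5.1 lists efficacy among the uses of the TVC and then states the grouping for the cohort. SAP 7.1 defines the study groups without limiting the definition to safety. VE in SAP 6.1.3 is one minus the ratio of the yearly rates in the 10-AS01E and Control groups, so it inherits that definition. No section of either document defines an efficacy analysis by allocated group.

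**Which errors matter?** Only a wrong product at Dose 1 moves a subject. A subject given the wrong product at Dose 2 alone keeps the Dose 1 group, which is then the allocated one.

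**The plan's own figure.** None exists for VE. The only sample-size figure (Protocol 11.4) is the chance of seeing at least one adverse event in 70 subjects. It reproduces: 1 − 0.99^70 = 50.5% (stated as above 50%) and 1 − 0.95^70 = 97.2% (stated as above 97%). It has no bearing on the grouping rule.

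**Size of the shift.** From the documents: 70 per group and one year of follow-up. Assumed: 1.5 exacerbations per subject-year in both groups (true VE of 0), hence 70 × 1.5 = 105 events per group as allocated, and complete follow-up. One Control-allocated subject with *e* events receives vaccine at Dose 1. Grouped as treated:

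rate ratio = [(105 + e)/71] ÷ [(105 − e)/69]

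| Events *e* | Vaccine rate | Control rate | Rate ratio | VE |
|---|---|---|---|---|
| 1.5 (average) | 106.5/71 = 1.500 | 103.5/69 = 1.500 | 1.000 | 0% |
| 2 | 107/71 = 1.507 | 103/69 = 1.493 | 1.010 | −1% |
| 4 | 109/71 = 1.535 | 101/69 = 1.464 | 1.049 | −5% |
| 6 | 111/71 = 1.563 | 99/69 = 1.435 | 1.090 | −9% |

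Grouped as allocated, the ratio is 105/105 = 1.00 in every row. The shift depends on how far the misdosed subject is from average: 4 events is 4/1.5 = 2.7 times the mean, and 6 is 4 times.

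**Other direction, more subjects.** Let *k* vaccine-allocated subjects receive placebo, each with *m* times the average rate, again at true VE of 0:

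VE = 1 − [(70 − km)/(70 − k)] ÷ [(70 + km)/(70 + k)]

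- k = 1, m = 2: 2.8%
- k = 3, m = 3: 1 − (61/67)/(79/73) = 15.9%
- k = 3, m = 0.5: 1 − (68.5/67)/(71.5/73) = −4.4%
- any k, m = 1: 0%

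**Sampling error for scale.** SAP 7.1.3 says "All CI computed will be two-sided 95% CI". With rate *r* and negative binomial dispersion *d* (both assumed), the standard error of the log rate ratio is √[2(1/(70r) + d/70)]. At VE of 0:

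- r = 2, d = 0.5: √0.0286 = 0.169, giving a VE interval of −39% to 28%
- r = 0.3, d = 1: √0.1238 = 0.352, giving −99% to 50%

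**Cost of grouping by allocation.** If misdosing is unrelated to risk, true VE is 50% and one vaccine-allocated subject gets placebo, the ratio as allocated is (69 × 0.5 + 1)/70 = 0.507, so VE is 49.3%. With five such subjects it is (65 × 0.5 + 5)/70 = 0.536, so VE is 46.4%. As-treated grouping stays at 50% in both cases.

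**The case against.** The case against giving this much weight is strong.

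- **The problem is hypothetical.** The documents report no product error. The SAP does record that some subjects completed paediatric diary cards. A reader might infer from this that dosing errors also happened, but it was a form mix-up and says nothing about product.
- **There are safeguards.** A reader might take replacement vials as a source of error. Protocol 7.4 points the other way: SBIR matches the replacement to the assigned formulation. Treatment numbers come from the system at both doses. The products do look different and only one is reconstituted (Protocol 6.3), but a separate unblinded team prepares and gives them.
- **The TVC VE is contingent.** It runs only above the 10% trigger and complements the ATP result. HRQOL, lung function and exercise capacity are TVC-first, but they receive descriptive statistics only.
- **The stakes are low.** Efficacy is tertiary, and Protocol 11.13 calls the comparisons descriptive and to be read with caution. The AECOPD model also adjusts for exacerbation history, COPD status, age and country.
- **As-treated grouping has a rationale.** For an exploratory estimate of biological effect it avoids dilution.

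All of this stands, and it limits the priority. It does not supply an analysis by allocated group, and covariate adjustment cannot restore balance on unmeasured factors.

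**Conclusion.** The point holds as a conditional, low-priority gap. Both documents group every analysis by the product given at Dose 1, and no planned efficacy analysis would keep a subject misdosed at Dose 1 in the allocated group. That the ATP efficacy cohort drops such a subject is probable rather than certain, because the form listing the elimination codes is not among the documents.

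The size is nil if nobody is misdosed at Dose 1. Under the assumptions above, one Control-allocated subject given vaccine moves the rate ratio by nothing (average event count) to 0.09 (six events). Shifts reach about 16 VE points only with three misdosed subjects at three times the average rate. The single-subject shifts are small beside intervals that run at least from −39% to 28%. The event rate, dispersion, number misdosed and relative risk are all assumptions; the documents give none of them.

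A reader might infer that the trial's main VE is already a non-randomised or biased comparison. The documents do not support that. The main VE is on the ATP cohort, the TVC version is contingent, only Dose 1 errors count, and none is reported. Nor is the TVC VE an all-subjects estimate: it covers vaccinated subjects with efficacy data.

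**What to change.** Keep the as-treated sentences in SAP 5.1 and 7.1 and Protocol 11.5.1 and 11.6 as the general rule, and add an exception:

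> *except that TVC analyses of AECOPD/VE, HRQOL, lung function and exercise capacity are performed by the group allocated by SBIR; any Dose 1 discrepancy between allocated and administered treatment will be listed.*

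An exception is better than a replacement, because the immunogenicity, biomarker and ATP analyses also rely on the general rule for their grouping. Sputum is left out of the list because SAP 6.1.7 names no cohort for it.

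The cost is one clause in each place and one listing. SBIR holds the allocated group and the eCRF records each treatment number, so no new data are needed. The statistical price is slight dilution if misdosing occurs and is unrelated to risk (50% to 49.3% with one misdosed subject).

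The change restores grouping by allocation, not a full intention-to-treat analysis. Counting still starts one month after Dose 2, and SAP 7.1.3 still leaves subjects with an exacerbation but no exacerbation sputum out of the NTHi-associated analyses.
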